7.3 PLANNED ANALYSES

The efficacy analysis will be performed in all randomized patients who were documented to have received any dose of trial medication and who have both baseline and any evaluable post-baseline measurement for at least one of the efficacy endpoints. This set will be called Full Analysis Set (FAS). The FAS definition will be fully specified or updated in the trial statistical analysis plan (TSAP).

For efficacy and safety analyses, patients will be analysed according to their planned treatment group.

7.3.1 Primary endpoint analyses

The primary endpoint will be analysed using an ANCOVA model including the fixed, categorical effect of treatment and the fixed continuous effect of baseline.

Significance tests will be based on adjusted means using a two-sided $\alpha = 0.05$ (two-sided 95% confidence intervals).

The primary analysis will be performed on the FAS within the optimal and sub-optimal PIFR groups, respectively. Patients will be analysed according to the PIFR stratum to which they belong (regardless of any misassignment to treatment based on identification of the wrong stratum), as such an error occurs before randomization and is therefore consistent with regulatory guidance.

To assess the homogeneity of the treatment effect on the primary endpoint across the levels of PIFR subgroups, the same ANCOVA model as in the primary analysis will be fitted in the overall population but replacing the treatment term by a treatment-by-PIFR subgroup term. A

Proprietary confidential information © 2020 Boehringer Ingelheim International GmbH or one or more of its affiliated companies

descriptive p-value of treatment effect homogeneity at week 4 will be calculated. No overall treatment effect will be estimated from this model as it is not interpretable.

Similarly, the same ANCOVA model as in the primary analysis will be fitted in the overall population but replacing the treatment term by a treatment-by-continuous baseline PIFR term. A descriptive p-value of treatment effect homogeneity at week 4 will be calculated. No overall treatment effect will be estimated from this model as it is not interpretable.

The results of the analysis of the primary endpoints for tiotropium + olodaterol FDC within the optimal and sub-optimal PIFR groups will be presented in a forest plot and the treatment by PIFR subgroup interaction p-value will be provided. Sensitivity analysis will be performed by including additional covariates such as severity, gender and age in the model to adjust for potential differences in prognostic factors between sub-optimal and optimal PIFR subgroups.

[figure not shown]
7.3.2 Secondary endpoint analyses

The key secondary endpoint will be analysed using the restricted maximum likelihood (REML) based approach using a mixed model with repeated measurements (MMRM). The analysis will be performed on the FAS within the optimal and sub optimal PIFR groups, respectively.

The analysis will include the fixed, categorical effect of treatment at each visit and the fixed continuous effect of baseline at each visit. Visits will be treated as repeated measures with an unstructured covariance structure used to model the within-patient measurements.

The Kenward-Roger approximation will be used to estimate denominator degrees of freedom and adjust standard errors. Significance tests will be based on least-squares means using a two-sided $\alpha = 0.05$ (two-sided 95% confidence intervals).

A selected set of analyses as that of the primary endpoint will be performed on the key secondary endpoint as well.

7.3.4 Safety analyses

Adverse events will be coded using the Medical Dictionary for Regulatory Activities (MedDRA) coding dictionary. Standard BI summary tables and listings will be produced. All adverse events with an onset between start of treatment and end of the REP, a period of 21 days after the last dose of trial medication, will be assigned to the treatment period for evaluation. All randomized patients who have taken at least one dose of study drug (i.e., the

treated set) will be included in the safety analysis. In general, safety analyses will be descriptive in nature and will be based on BI standards. No hypothesis testing is planned.

Statistical analysis and reporting of adverse events will concentrate on treatment-emergent adverse events. To this end, all adverse events occurring between start of treatment and end of the residual effect period will be considered 'treatment-emergent'. The residual effect period is defined as 21 days. Adverse events that start before first drug intake and deteriorate under treatment will also be considered as 'treatment-emergent'.

Frequency, severity, and causal relationship of adverse events will be tabulated by system organ class and preferred term after coding according to the current version of MedDRA.

All treated patients will be included in the safety analysis. In general, safety analyses will be descriptive in nature and will be based on BI standards. No hypothesis testing is planned.

Laboratory data will be analysed both quantitatively as well as qualitatively. The latter will be done via comparison of laboratory data to their reference ranges. Values outside the reference range as well as values defined as clinically relevant will be summarized.

Treatment groups will be compared descriptively with regard to distribution parameters as well as with regard to frequency and percentage of patients with abnormal values or clinically relevant abnormal values.

Vital signs, physical examinations, or other safety-relevant data observed at screening, baseline, during the course of the trial and at the end-of-trial evaluation will be assessed with regard to possible changes compared to findings before start of treatment.

7.3.5 Interim Analyses

An interim analysis is not planned in this clinical trial.

7.4 HANDLING OF MISSING DATA

Missing completely at random is assumed for the primary endpoint as very little missing data is expected and no imputation will be performed. The REML-based MMRM model described in [section 7.3.2](#) will handle missing data due to early drop outs or missing data in between visits which are assumed to be missing at random. Additional details on the imputation of missing data will be specified in the TSAP prior to unblinding.

7.5 RANDOMIZATION

Approximately 200 patients will be randomized in blocks to double-blind treatment stratified by PIFR optimal and sub-optimal subgroups. Approximately equal numbers of patients will be randomized to each treatment group (50 in tiotropium + olodaterol Respimat® and 50 in placebo Respimat® for each PIFR subgroup). BI will arrange for the randomization and the packaging and labelling of trial medication. The randomization list will be generated using a validated system, which involves a pseudo-random number generator so that the resulting treatment will be both reproducible and non-predictable. The block size will be documented in the Clinical Trial Report. Access to the codes will be controlled and documented.

7.6 DETERMINATION OF SAMPLE SIZE

From previous studies, an appropriate estimate of the standard deviation (SD) for change from baseline in $\text{FEV}_1 \text{ AUC}_{0-3h}$ ($\Delta \text{FEV}_1 \text{ AUC}_{0-3h}$) and trough FEV_1 (ΔTFEV_1) is 210 mL ([c02098902-03](#), [c02037872-05](#)). Based on an assumed treatment difference of 260 ml in $\Delta \text{FEV}_1 \text{ AUC}_{0-3h}$ and 140 ml in ΔTFEV_1 between tiotropium + olodaterol Respimat® and placebo Respimat®, two-sided alpha of 0.05 and SD of 210 ml, a total of 98 patients will provide 99% power within the optimal and sub-optimal PIFR subpopulations for FEV_1 , AUC_{0-3h} and 90% power for trough FEV_1 . The results of power calculations are shown in Tables 7.6: 1 and [7.6: 2](#). From previous studies ([c02098902-03](#), [c02037872-05](#)), the discontinuation rate is assumed to be low within the first 2-4 weeks.

Therefore, a sample size of 200 patients overall with 1:1 randomization ratio and 100 within each subpopulation (100 in optimal PIFR and 100 in sub-optimal PIFR) will provide adequate power to detect a treatment difference of 260 ml for $\text{FEV}_1 \text{ AUC}_{0-3h}$ and to detect a treatment difference of 140 ml for trough FEV_1 .

Table 7.6: 1 Sample size to achieve 90% power assuming two-sided alpha=0.05 and standard deviation of 210 ml

Power	Difference in ΔTFEV_1	SD	N Total
90%	120 ml	210 ml	132
90%	130 ml	210 ml	112
90%	140 ml	210 ml	98
90%	150 ml	210 ml	86
90%	160 ml	210 ml	76
Power	Difference in $\Delta \text{FEV}_1 \text{ AUC}_{0-3h}$	SD	N Total
90%	260 ml	210 ml	30
90%	280 ml	210 ml	26
90%	300 ml	210 ml	24

Proprietary confidential information © 2020 Boehringer Ingelheim International GmbH or one or more of its affiliated companies

Table 7.6: 2 Power for given sample size of 98 patients assuming a two-sided alpha=0.05 and standard deviation of 210 ml

Difference in ΔTFEV_1	SD	N Total	Power
120 ml	210 ml	98	80%
130 ml	210 ml	98	86%
140 ml	210 ml	98	90%
Difference in $\Delta\text{FEV1 AUC}_{0-3h}$	SD	N Total	Power
260 ml	210 ml	98	>99%
280 ml	210 ml	98	>99%
300 ml	210 ml	98	>99%

Calculations were performed using SAS PROC POWER in SAS v9.4.

8. INFORMED CONSENT, TRIAL RECORDS, DATA PROTECTION, PUBLICATION POLICY, AND ADMINISTRATIVE STRUCTURE

The trial will be carried out in compliance with the protocol, the ethical principles laid down in the Declaration of Helsinki, in accordance with the ICH Harmonized Guideline for GCP, relevant BI Standard Operating Procedures (SOPs), the EU directive 2001/20/EC / EU regulation 536/2014. Investigators and site staff must adhere to these principles. Deviation from the protocol, the principles of ICH GCP or applicable regulations as will be treated as protocol deviation.

Standard medical care (prophylactic, diagnostic and therapeutic procedures) remains the responsibility of the treating physician of the patient.

The investigator will inform the sponsor immediately of any urgent safety measures taken to protect the trial patients against any immediate hazard, as well as of any serious breaches of the protocol or of ICH GCP.

The Boehringer Ingelheim transparency and publication policy can be found on the following web page: trials.boehringer-ingelheim.com. The rights of the investigator and of the sponsor with regard to publication of the results of this trial are described in the investigator contract.

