Statistical methods	The primary endpoint will be analysed using an ANCOVA model in PIFR optimal and sub-optimal groups separately. The ANCOVA model will include the fixed, categorical effect of the treatment and the fixed continuous effect of baseline. The key secondary endpoint will be analysed using restricted maximum likelihood (REML) based

	
mixed effects model repeated measures (MMRM) approach because data are available at an additional visit. The MMRM model will include the fixed, categorical effect of treatment at each visit, and the fixed continuous effect of baseline at each visit. The primary endpoint will be compared across treatment groups in PIFR subgroups (first optimal and then sub-optimal). Then the key secondary endpoint will be compared across treatment groups in the PIFR subgroups in the same order. The entire hierarchical hypothesis testing strategy for tiotropium + olodaterol FDC (5μg/5μg) versus placebo in PIFR subgroups will be protected at an overall two-sided 0.05 type I error rate.

--	---

FLOW CHART

Trial Periods	Screening	Treatment			Follow-up
Visit	1 ¹	2	3	4 ² (EOT)	5 (Phone call)
Days	-3 to -14	1	15	29	50
Week	-2	0	2	4	7
Time window for visits	NA	NA	±2 days	±2 days	+ 7 days
Informed consent ³	X				
Demographics/baseline conditions	X				
Medical history	X				
Physical examination & vital signs ⁴	X	X		X	
Register patient in IRT ⁵	X	X		X	
Medication washout check ⁶		X	X	X	
Pulmonary function tests ⁷	X	X	X	X	
Plethysmography ⁸	X	X			
Laboratory tests (safety) ⁹	X	X		X	
eGFR ¹⁰	X				
Pregnancy test ¹¹	X	X	X	X	
12 lead-ECG ¹²	X	X		X	
Review of in-/exclusion criteria	X	X			
Dispense [REDACTED] & paper patient diary	X				
[REDACTED] training ¹⁴	X	X	X		
PIFR measurements at clinic ¹⁵	X	X	X	X	
Dispense rescue medication ¹⁶	X	X	X		
Collect rescue medication		X	X	X	
Training in the use of Respimat® ¹⁷		X	X		
Randomization ¹⁸		X			
Administration of trial medication in clinic		X	X	X	
Dispense trial medication ¹⁹		X			
Collect trial medication				X	
AEs/SAEs*****	X	X	X	X	X
Medication compliance check ²⁰			X	X	
Concomitant therapy	X	X	X	X	X
Trial completion					X ²¹

Footnotes:

1. The interval between visits 1 and 2 (screening period) can be extended for up to 2 weeks for administrative reasons ([section 6.2.1](#)).

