7.2 NULL AND ALTERNATIVE HYPOTHESES

The following hypotheses will be tested in the study on the primary and key secondary endpoints. Each hypotheses will be tested in hierarchical order at 5% level of significance (two-sided) to protect the overall type I error at 5% (two-sided). The baseline value will be the measurement made prior to the first dosing at Visit 2.

- H₀₋₁: Mean FEV₁ AUC_{0-3h} change from baseline (tiotropium + olodaterol via Respimat®) = Mean FEV₁ AUC_{0-3h} change from baseline (Placebo) in the optimal PIFR group at 4 weeks

vs.

H₁₋₁: Mean FEV₁ AUC_{0-3h} change from baseline (tiotropium + olodaterol via Respimat®) ≠ Mean FEV₁ AUC_{0-3h} change from baseline (Placebo) in the optimal PIFR group at 4 weeks.

- H₀₋₂: Mean FEV₁ AUC_{0-3h} change from baseline (tiotropium + olodaterol via Respimat®) = Mean FEV₁ AUC_{0-3h} change from baseline (Placebo) in the sub-optimal PIFR group at 4 weeks

vs.

H₁₋₂: Mean FEV₁ AUC_{0-3h} change from baseline (tiotropium + olodaterol via Respimat®) ≠ Mean FEV₁ AUC_{0-3h} change from baseline (Placebo) in the sub-optimal PIFR group at 4 weeks.

- H₀₋₃: Mean trough FEV₁ change from baseline (tiotropium + olodaterol via Respimat®) = Mean trough FEV₁ change from baseline (Placebo) in the optimal PIFR group at 4 weeks

vs.

$H_{1.3}$: Mean trough FEV₁ change from baseline (tiotropium + olodaterol via Respimat[®]) ≠ Mean trough FEV₁ change from baseline (Placebo) in the optimal PIFR group at 4 weeks.

- $H_{0.4}$: Mean trough FEV₁ change from baseline (tiotropium + olodaterol via Respimat[®]) = Mean trough FEV₁ change from baseline (Placebo) in the sub-optimal PIFR group at 4 weeks

vs.

$H_{1.4}$: Mean trough FEV₁ change from baseline (tiotropium + olodaterol via Respimat[®]) ≠ Mean trough FEV₁ change from baseline (Placebo) in the sub-optimal PIFR group at 4 weeks.

Each of the tests will only be considered confirmatory if all previous tests are successful, i.e. the hypotheses tests were significant at 2-sided 5% level and the treatment effect favored tiotropium + olodaterol over placebo in each PIFR subgroup.

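### Does the 90% trough FEV1 power in Protocol section 7.6 overstate the power of the last test in the fixed sequence?

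*Protocol*

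**What the plan says.** Protocol section 7.6 takes an SD of 210 mL for both endpoints and treatment differences of 260 mL for FEV1 AUC0-3h and 140 mL for trough FEV1. It then says: "two-sided alpha of 0.05 and SD of 210 ml, a total of 98 patients will provide 99% power", with the claim applying "within the optimal and sub-optimal PIFR subpopulations for FEV_1 , AUC_{0-3h} and 90% power for trough FEV_1". Table 7.6: 2 gives trough power at N = 98 as 80%, 86% and 90% for 120, 130 and 140 mL, and AUC power as above 99%. Each row has one difference, one SD and one total N, and the calculations are attributed to SAS PROC POWER. The section concludes that 100 patients per stratum give adequate power for the two stated differences.

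Protocol section 7.2 lists the hypotheses: H0-1 (AUC, optimal), H0-2 (AUC, sub-optimal), H0-3 (trough, optimal) and H0-4 (trough, sub-optimal), each at two-sided 5%. "Each of the tests will only be considered confirmatory if all previous tests are successful". The synopsis has the same order: after the primary endpoint, "Then the key secondary endpoint will be compared across treatment groups in the PIFR subgroups in the same order".

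Neither document reports power for the sequence. The SAP (section 3) refers the reader to the protocol for sample size.

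**The concern.** A fixed sequence protects the type I error without splitting alpha, but later tests pay for it in power: a test cannot be confirmatory if an earlier one fails. H0-4 comes fourth, behind a trough test with only about 90% power of its own. Someone who reads the sample-size section alone could take 90% as the chance of a confirmatory trough result in each stratum. For the sub-optimal stratum that is too high.

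The sub-optimal stratum is also the one of most interest, since the trial's rationale is that patients may benefit whatever inspiratory flow they can generate. If the sponsor had relied on 90% for that claim, the trial would be smaller than intended for it.

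**Working it through.** **Inputs** (Protocol sections 7.2, 7.5 and 7.6): two-sided alpha 0.05 for each test; SD 210 mL; differences of 260 mL (AUC) and 140 mL (trough); N = 98 per stratum (49 per arm) for the power table and 100 (50 per arm) as planned; no dropout rate given.

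**Step 1: reproduce the plan's figures.** For a two-sample t-test with n per arm, the non-centrality is δ / (SD × √(2/n)) on 2n − 2 degrees of freedom.

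- Standard error at n = 49: 210 × √(2/49) = 42.43 mL.
- Trough, 140 mL: 140 / 42.43 = 3.30, power 90.4% (stated: 90%).
- AUC, 260 mL: 260 / 42.43 = 6.13, power 99.998% (stated: 99% in the text, above 99% in the table).

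The same formula returns all eight sample sizes in Table 7.6: 1 exactly (132, 112, 98, 86, 76, 30, 26, 24). The protocol's arithmetic is therefore correct, and it is single-test arithmetic.

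**Step 2: carry the tests through the sequence.** The strata contain different patients and are analysed separately, so results in one are independent of results in the other. Writing a for AUC power and p for trough power:

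- H0-1 and H0-2 both succeed: a² = 0.99998² = 0.99996.
- H0-3 confirmatory: a² × p = 0.99996 × 0.9043 = 0.9043.
- H0-4 confirmatory (all four succeed): a² × p² = 0.99996 × 0.9043² = 0.818.

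These products treat AUC and trough as independent within a stratum, which they are not. The correlation is not given, but it hardly matters. Within a stratum the joint success probability lies between a + p − 1 = 0.90432 and p = 0.90434. Squared, that is 0.81779 to 0.81783, a range of 0.004 percentage points. Simulation with 200,000 trials at assumed correlations of 0, 0.5, 0.8 and 0.95 gave 81.7% to 81.8%.

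| Trough difference | Table 7.6: 2 | Per test, N = 98 | H0-4 in sequence, N = 98 | Per test, N = 100 | H0-4 in sequence, N = 100 |
|---|---|---|---|---|---|
| 140 mL | 90% | 90.4% | 81.8% | 91.0% | 82.8% |
| 130 mL | 86% | 85.8% | 73.7% | 86.5% | 74.9% |
| 120 mL | 80% | 80.0% | 63.9% | 80.8% | 65.2% |

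The loss at 140 mL and N = 98 is 90.4 − 81.8 = 8.6 points, almost all of it from H0-3 standing ahead of H0-4.

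**Step 3: how firm is 82%?** The planned trough model adjusts for baseline: "The analysis will include the fixed, categorical effect of treatment at each visit and the fixed continuous effect of baseline at each visit". The protocol does not say whether 210 mL already reflects that. If it does not, the residual SD is 210 × √(1 − r²), where r is the correlation between baseline and change. As assumptions, r of about 0.30 gives an SD near 200 mL and H0-4 power of 86.3% at N = 98; r of about 0.43 gives an SD near 190 mL and 90.4%. If 210 mL is already adjusted, 81.8% stands.

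**Step 4: compare with the claim.** Section 7.6 gives power within each subpopulation for a stated difference, SD and alpha. It does not mention the hierarchy, a confirmatory result or success on all four tests. With power above 99.9% for both primary tests, about 90% for H0-3 and about 82% for H0-4, its conclusion of adequate power still holds.

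**The case for a change.** The case for a change is that trough FEV1 sets the sample size: Table 7.6: 1 needs 98 patients for trough at 140 mL but only 30 for AUC at 260 mL. The 90% is thus the figure that justifies the trial's size, and it is quoted for both strata without a per-test label. Protocol section 3.2 admits that nothing is known about the effect in the two PIFR populations, so the 120 and 130 mL rows are real possibilities, and there the sequence figure falls to about 64% and 74%. Only two patients per stratum separate 98 from 100; at an assumed 45 evaluable per arm, H0-4 power at 140 mL is about 77%. One sentence would disclose all this.

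The numbers stand, and a hurried reader could misread the 90%. What does not follow is that the plan needs correcting. Single-test power is the usual form for such a table, the layout makes it recognisable, and the testing order is disclosed in the synopsis and section 7.2, so the product is easy to derive. Missing data and smaller effects also lower the per-test figures, so they are not specific to the hierarchy. The proposed sentence would itself assume equal effects in both strata, which the protocol says it cannot know. Nor is any decision shown to depend on it: holding H0-4 at 90% through the sequence would take about 60 per arm per stratum, or 240 patients in all, and even the case for a change does not ask for that.

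**Conclusion.** No change. The 90% is correct for what it describes, a single trough comparison within one stratum. The probability that H0-4 is confirmatory, which is also the probability that all four tests succeed, is about 82% with 98 per stratum and 83% with 100. This assumes 140 mL in both strata, an SD of 210 mL with no further gain from baseline adjustment, and no dropout beyond the N used. It is an unreported quantity for the last of four tests, on the key secondary endpoint. If H0-3 fails, H0-4 loses only its confirmatory status; its estimate and confidence interval are unaffected. Type I error control, both primary tests and H0-3 are as the protocol presents them. A colleague who wants the sequence figure can square the per-test power; the plan reads and runs the same either way.

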8.1 TRIAL APPROVAL, PATIENT INFORMATION, INFORMED CONSENT

This trial will be initiated only after all required legal documentation has been reviewed and approved by the respective IRB / Independent Ethics Committee (IEC) and competent authority according to national and international regulations. The same applies for the implementation of changes introduced by amendments.

Prior to patient participation in the trial, written informed consent must be obtained from each patient according to ICH-GCP and to the regulatory and legal requirements of the participating country. Each signature must be personally dated by each signatory and the informed consent and any additional patient-information form retained by the investigator as part of the trial records. A signed copy of the informed consent and any additional patient information must be given to each patient. The patient must be given sufficient time to consider participation in the trial. The investigator or delegate obtains written consent of the patient's own free will with the informed consent form after confirming that the patient understands the contents. The investigator or [redacted] delegate must sign (or place a seal on) and date the informed consent form.

Re-consenting may become necessary when new relevant information becomes available and should be conducted according to the sponsor's instructions. The consent and re-consenting process should be properly documented in the source documentation.

8.2 DATA QUALITY ASSURANCE

A risk-based approach is used for trial quality management. It is initiated by the assessment of critical data and processes for trial subject protection and reliability of the results as well as identification and assessment of associated risks. An Integrated Quality and Risk Management Plan documents the rationale and strategies for risk management during trial conduct including monitoring approaches, vendor management and other processes focusing on areas of greatest risk.

Continuous risk review and assessment may lead to adjustments in trial conduct, trial design or monitoring approaches.

A quality assurance audit/inspection of this trial may be conducted by the sponsor, sponsor's designees, or by IRB / IEC or by regulatory authorities. The quality assurance auditor will have access to all medical records, the investigator's trial-related files and correspondence, and the informed consent documentation of this clinical trial.

